5.4.5 PK, PD, or Biomarker Analyses

[CCI]

6.0 ASSESSMENT OF SAFETY

Safety assessments will consist of monitoring and recording AEs and SAEs; measurements of protocol-specified hematology, clinical chemistry, urinalysis, and other laboratory variables; measurement of protocol-specified vital signs; and other protocol-specified tests that are deemed critical to the safety evaluation of the study drug(s).

6.1 DEFINITIONS

6.1.1 Adverse Events

An AE is any unfavorable and unintended sign, symptom, or disease temporally associated with the use of an investigational (medicinal) product or other protocol-imposed intervention, regardless of attribution.

This includes the following:

- AEs not previously observed in the subject that emerge during the protocol-specified AE reporting period, including signs or symptoms associated with GBM that were not present before the AE reporting period (see [Section 6.2.1](#)).
- Pre-existing medical conditions (other than the condition being studied) judged by the investigator to have worsened in severity or frequency or changed in character during the protocol-specified AE reporting period.
- Abnormal laboratory values considered clinically significant by the investigator should be reported as an AE.

The following are NOT considered an AE:

- **Pre-existing condition that has not worsened:** A pre-existing condition (documented on the medical history eCRF) is not considered an AE unless the severity, frequency, or character of the event worsens during the study period.
- **Preplanned hospitalization:** A hospitalization planned before signing the ICF is not considered an SAE, but rather a therapeutic intervention. However, if during the preplanned hospitalization an event occurs, which prolongs the hospitalization or meets any other SAE criteria, the event will be considered an SAE. Surgeries or interventions that were under consideration but not performed before signing the ICF will not be considered serious if they are performed after signing the ICF for a condition that has not changed from its baseline level. Elective hospitalizations for social reasons, solely for the administration of chemotherapy, or due to long travel distances, are also not SAEs.

- **Diagnostic testing and procedures:** Testing and procedures should not be reported as AEs or SAEs but rather the cause for the test or procedure should be reported. If a test or procedure is done to rule out a diagnosis, the sign or symptom leading to the test/procedure should be the event term and the event term should only be updated to the diagnosis if/when the diagnosis is confirmed. Testing and procedures performed solely as screening measures (e.g., routine screening mammography or colonoscopy) should not be reported as AEs or SAEs.
- **Abnormal laboratory results that the investigator considers to not be clinically significant:** Abnormal laboratory results are not AEs unless they are clinically significant. For example, a clinically significant laboratory result is one that requires treatment (e.g., a blood transfusion for low hemoglobin) or requires a change in study drug (e.g., lowering the dose or withholding study drug while the laboratory finding resolves or stabilizes).
- **Progression of underlying malignancy:** Progression of underlying malignancy will not be reported as an AE if it is clearly consistent with the suspected progression of the underlying cancer. Hospitalization due solely to the progression of underlying malignancy should NOT be reported as an SAE. Clinical symptoms of progression may be reported as AEs if the symptoms cannot be determined as exclusively due to the progression of the underlying malignancy or if they do not fit the expected pattern of progression for the disease under study.

Symptomatic deterioration may occur in some subjects. Symptomatic deterioration is when progression is evident in the subject's clinical symptoms and the investigator may elect not to perform further disease assessments.

If there is any uncertainty about an AE being due only to the disease under study, it should be reported as an AE or SAE.

6.1.2 Serious Adverse Event

The terms "severe" and "serious" are not synonymous. Severity (or intensity) refers to the grade of an AE (see below). "Serious" is a regulatory definition and is based on subject or event outcome or action criteria usually associated with events that pose a threat to a subject's life or functioning. Seriousness (not severity) serves as the guide

for defining regulatory reporting obligations from the sponsor to applicable regulatory authorities.

An AE should be classified as an SAE if it meets any 1 of the following criteria:

- It results in death (i.e., the AE actually causes or leads to death)
- It is life-threatening (i.e., the AE, in the view of the investigator, places the subject at immediate risk of death. It does not include an AE that, had it occurred in a more severe form, might have caused death).
- It requires or prolongs inpatient hospitalization
- It results in persistent or significant disability/incapacity (i.e., the AE results in substantial disruption of the subject's ability to conduct normal life functions)
- It results in a congenital anomaly/birth defect in a neonate/infant born to a mother exposed to the investigational product
- It is considered a significant medical event by the investigator based on medical judgment (e.g., may jeopardize the subject or may require medical/surgical intervention to prevent 1 of the outcomes listed above)

6.1.3 Adverse Events of Special Interest

The following events are adverse events of special interest (AESIs) and must be reported to the sponsors expeditiously (see [Section 6.2.5](#) for reporting instructions), irrespective of regulatory seriousness criteria or causality:

- *Ventricular arrhythmias (e.g., ventricular extrasystoles, ventricular tachycardia, ventricular arrhythmia, ventricular fibrillation, etc.)*

6.1.4 Severity

Definitions found in the CTCAE version 4.03 or higher will be used for grading the severity (intensity) of AEs. The CTCAE displays Grades 1 through 5 with unique clinical descriptions of severity for each referenced AE. Should a subject experience any AE not listed in the CTCAE, the following grading system should be used to assess severity:

- Grade 1 (Mild AE) – experiences that are usually transient, requiring no special treatment, and not interfering with the subject's daily activities
- Grade 2 (Moderate AE) – experiences that introduce some level of inconvenience or concern to the subject, and which may interfere with daily activities, but are usually ameliorated by simple therapeutic measures
- Grade 3 (Severe AE) – experiences that are unacceptable or intolerable, significantly interrupt the subject's usual daily activity, and require systemic drug therapy or other treatment

- Grade 4 (Life-threatening or disabling AE) – experiences that cause the subject to be in imminent danger of death
- Grade 5 (Death related to AE) – experiences that result in subject death

6.2 DOCUMENTING AND REPORTING OF ADVERSE AND SERIOUS ADVERSE EVENTS

The investigator is responsible for ensuring that all AEs and SAEs that are observed or reported during the study, as outlined in the prior sections, are recorded on the eCRF. All SAEs must be reported on the SAE form or clinical database.

6.2.1 Adverse Event Reporting Period

After the signing of the ICF *and prior to the first dose of study drug*, all SAEs must be reported. After the first dose of study drug, all AEs/SAEs, irrespective of attribution of causality, must be reported.

All AEs will be reported until 30 days after the last dose of study drug or the start of new anticancer therapy (whichever comes first). After this period, investigators should report SAEs or other AEs of concern that are believed to be related to prior treatment with study drug.

All SAEs that occur during the reporting period should be followed to resolution or until the investigator assesses the subject as stable or until the subject is lost to follow-up or withdraws consent. Resolution/stable means the subject has returned to baseline state of health or the investigator does not expect any further improvement or worsening of the event.

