4.3 TREATMENT TERMINATION AND SAFETY FOLLOW-UP VISITS

A TT visit is required for safety assessments for any subjects who permanently discontinue study drug for any reason (except for death, lost to follow-up, or withdrawal of consent), including disease progression. The TT visit should be scheduled within 7 days of the last dose of study drug, if possible, and is not required for subjects who discontinue from the study treatment within 10 days of a scheduled study visit or if the TT visit would be performed within 14 days of the SFU visit.

In addition to the TT visit, each subject should be followed until the SFU visit at 30 (+7) days after his or her last dose of study drug to monitor for resolution or progression of AEs and to document the occurrence of any new events, regardless of whether the subject receives a new anticancer therapy or demonstrates disease progression within this timeframe. Subjects who withdraw consent for study treatment should still be encouraged to complete the SFU assessments, but these assessments cannot be mandated if subject consent for further study participation is withdrawn. If the TT visit and the SFU visit coincide, then these can be combined into 1 visit. The Schedule of Assessments ([Appendix 1](#)) describes the procedures required for the TT and SFU visits.

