5.4 ENDPOINT DATA ANALYSIS

5.4.1 Safety Endpoint

Verbatim descriptions of AEs will be mapped according to the MedDRA thesaurus terms and graded according to the National Cancer Institute (NCI) CTCAE, v4.03 or higher. Extent of exposure to study drug, all AEs, SAEs, non-SAEs leading to study drug discontinuation, and study drug-related AEs will be summarized. The frequency of AEs will be summarized by system organ class and preferred terms according to MedDRA,

as well as per severity per NCI CTCAE grade. Only treatment-emergent AEs will be summarized. For events with varying severity, the worst reported grade will be used.

Laboratory abnormalities will be defined based on laboratory normal ranges (universal normal ranges if central laboratory) and will be summarized by visit. Selected laboratory parameters may be analyzed with shift tables and summaries of changes from baseline to worst post-treatment value. Figures of changes in laboratory parameters over time may be generated, as appropriate, for certain labs.

Change from baseline in vital sign assessments will be tabulated and summarized.

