- Any subjects who are tolerating study drug and have not progressed at the end of trial, defined as 52 weeks after the last subject is enrolled to the study, may continue to receive their study treatment after discussion with the medical monitor. They will continue to have scheduled visits as outlined for Cycles 5+ on the schedule of assessments.
- A 30-day (+7 days) safety follow-up visit is required when subjects discontinue study drug. After the end of the protocol-defined adverse event reporting period (see Section 6.2.1), only serious adverse events considered related to study drug(s) or study procedures are required to be collected.
- Each subject should be followed until disease progression or the start of alternative anticancer therapy. If neither of these has occurred at the time of the 30-day SFU visit, DFU visits should occur approximately every 3 months (12 weeks) from date of last dose until disease progression or next anticancer treatment. During this period, subjects will be followed via MRIs.
- Once subjects progress or start use of alternative anticancer therapy—for all subjects who have not withdrawn consent—they will be contacted approximately every 3 months (12 weeks) from date of last dose by clinic visit or telephone, to assess survival and the use of alternative anticancer therapy until death or lost to follow-up.
- An MRI must be performed within 21 days before the administration of study drug; all other screening tests should be performed within 21 days before the first administration of study drug, unless otherwise indicated.

- f. The screening physical examination will include, at a minimum, the general appearance of the subject, height (screening only) and weight, and examination of the skin, eyes, ears, nose, throat, lungs, heart, abdomen, extremities, musculoskeletal system, lymphatic system, and nervous system. Symptom-directed physical examinations, including tumor assessments by palpation, are done thereafter.
- g. Vital signs (blood pressure, pulse, and temperature) will be assessed after the subject has rested in the sitting position.
- h. An ECG will be performed during screening. Subjects should be in supine position and resting for ≥ 10 minutes before the ECG.
- i. Women of childbearing potential only.
- j. This urine or serum pregnancy test is to be performed on Cycle 1 Day 1 (-3 days).

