### **10.6.1 Adverse Events**

The Medical Dictionary for Regulatory Activities (MedDRA v20.1 or later) will be used to code all AEs to a system organ class and a preferred term. The severity of the AE will be assessed by National Cancer Institute (NCI) Common Terminology Criteria for Adverse Events (CTCAE) Version 4.03. Study drug-related AEs are those assessed by investigator as related.

All AE tables will be summarized by treatment cohort.

TEAEs are defined as those events that occur or worsen on or after the first dose of study drug (acalabrutinib), through the treatment phase, and within 30 days following the last dose of acalabrutinib.

TEAEs will be summarized by system organ class (SOC) and preferred terms (PTs) as well as preferred terms only in descending order of frequency, by CTCAE severity grade.

Drug-related TEAEs, treatment-emergent serious adverse events (TESAEs), TEAEs leading to study drug discontinuation or dose modifications or dose delay will be summarized by PTs in descending order of frequency and by CTCAE severity grade.

Death information is reported in the study exit case report form (CRF) and death information CRF for all deaths. Incidences of deaths are to be reported, along with the primary cause of death.

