## **12.2 Imputation rules for partial or missing dates**

Imputation of partial dates will be made for AE onset and stop dates, start and end dates of concomitant medication, start date of subsequent anticancer therapy, date of initial diagnosis and death date. If dates are completely missing, no imputation will be made. For any partial date with missing year, no imputation will be made.

The general rule for imputation is:

- If only day is missing, then the 15th of the month will be used.
- If only year is present, then June 30th will be used.

If such imputation date for initial diagnosis is on or after date of first dose, then date of first dose – 1 will be used. If such imputed date for subsequent anticancer therapies is before date of last dose, then date of last dose + 1 will be used.

If the imputed date is for an AE start date and is in the same year and month as but before the first dose date, then the first dose date will be used, or if the imputed AE start date is after the AE end date, then the AE end date will be used. If the imputed date is for an AE start date and is in the same year and month as but after the last dose date + 30 days, then the last dose date + 30 days will be used.

If the imputed date is for an AE end date and is after the death date, then the death date will be used, or if the imputed AE end date is before the AE start date, then the AE start date will be used.

Every effort will be made to obtain complete dates for deaths. If both month and day are missing for death date or a death date is totally missing, do not impute and censor the subject survival time. If death year and month are available but day is missing, the following algorithm will be used:

- If mmyyyy for last contact date = mmyyyy for death date, set death date to the day after the last contact date.
- If mmyyyy for last contact date < mmyyyy for death date, set death date to the first day of the death month.
- If mmyyyy for last contact date > mmyyyy for death date, data error and do not impute.

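### For subjects who start new anticancer therapy within 30 days of last dose, the SAP's TEAE window does not match the protocol's AE reporting window, and protocol 4.3 and 6.2.1 disagree.

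*Protocol*

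**What the plan says.** **Protocol 6.2.1** requires all AEs, whatever their cause, to be reported "until 30 days after the last dose of study drug or the start of new anticancer therapy (whichever comes first"). It then continues with a narrower duty: "After this period, investigators should report SAEs or other AEs of concern that are believed to be related to prior treatment with study drug". Section 4.1.3 sends the reader to 6.2.1 for the reporting period. The Appendix 1 footnote on the safety follow-up (SFU) visit does the same, and says that once the period is over "only serious adverse events considered related to study drug(s) or study procedures are required to be collected".

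**Protocol 4.3** says that "each subject should be followed until the SFU visit at 30 (+7) days after his or her last dose of study drug". The stated purpose includes recording any new events, "regardless of whether the subject receives a new anticancer therapy or demonstrates disease progression within this timeframe".

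**SAP 10.6.1** defines TEAEs as events that start or worsen from first dose, through treatment, and "within 30 days following the last dose of acalabrutinib". **SAP 12.2** uses the same limit for partial AE start dates. If the imputed date falls in the same month as, but "after the last dose date + 30 days, then the last dose date + 30 days will be used". Neither SAP section mentions new anticancer therapy.

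**Protocol 5.4.1** makes the TEAE definition decisive for the safety tables: "Only treatment-emergent AEs will be summarized".

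**The concern.** Safety is a primary objective, and the TEAE tables are its main output. A TEAE window is sound only if events are collected in the same way throughout it. Here the SAP window assumes complete collection to day 30. The section that governs reporting allows complete collection to end sooner, and the section on follow-up visits says that it does not.

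The affected situation is foreseeable. Protocol 3.0 and 3.10 list the start of another anticancer therapy among the reasons for stopping study treatment. For such a subject, full reporting under 6.2.1 may end close to the last dose, while the SAP keeps counting for 30 days.

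The error can run either way, and the plan's own content gives examples:

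- **Events from the next regimen.** Subjects have not had bevacizumab (exclusion criterion 24). Protocol 1.1 associates that drug with hypertension, and SAP 12.5.1 lists hypertension as an event of clinical interest. If bevacizumab were the next therapy, hypertension first arising on it within the 30 days would be tabulated as treatment-emergent on acalabrutinib.
- **Events not reported.** SAP 12.5.2 counts CNS hemorrhage of any grade as major. A low-grade, non-serious bleed judged unrelated, and occurring after new therapy began, need not be reported under 6.2.1.

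**Working it through.** The plan states no figure on this point, so there is none to reproduce. The check sets the windows side by side, follows one subject through them, and then sizes a single misclassified event.

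**1. The windows**

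| Source | End of window | Effect of new anticancer therapy |
|---|---|---|
| Protocol 6.2.1, all AEs | Last dose + 30 days, or new therapy if earlier | Ends complete reporting |
| Protocol 6.2.1, afterwards | Not limited | SAEs or other AEs of concern believed related |
| Appendix 1 footnote, afterwards | Not limited | Related SAEs only, so narrower than 6.2.1 |
| Protocol 4.3 | SFU visit at 30 (+7) days | None: new events still documented |
| SAP 10.6.1 | Last dose + 30 days | Not mentioned, so no cut |
| SAP 12.2, cap on imputed AE start | Last dose + 30 days | Not mentioned, so no cut |

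**2. One subject who starts new therapy on day t after last dose (t < 30)**

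The stretch in which the SAP counts TEAEs but 6.2.1 no longer requires all AEs is 30 − t days. If t = 14, an assumed value for illustration, this is 30 − 14 = 16 days. A new event in that stretch is handled as follows:

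- *Site follows 6.2.1, event judged unrelated.* It need not be reported. The TEAE tables lack an event that falls inside the SAP definition.
- *Site follows 6.2.1, event judged related, and serious or of concern.* It is reported and counted. Late events therefore reach the tables through a causality filter, which raises the drug-related share among them.
- *Site follows 4.3.* The event is documented whatever its cause and counted as an acalabrutinib TEAE, even though it arose on another regimen.

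For a subject who starts no new therapy within 30 days, all the windows reach last dose + 30 days and the conflict has no effect.

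**3. Size of one misclassified event**

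SAP 10.1 presents summaries by cohort. SAP 3.2 gives 15 subjects at 200 mg BID and 9 at 400 mg QD. Incidence is subjects with the event divided by cohort size, so one subject changes it by:

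- 200 mg BID: 1/15 = 0.067, or 6.7 percentage points
- 400 mg QD: 1/9 = 0.111, or 11.1 percentage points

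This applies when the subject had not already had the same preferred term on treatment. If the subject had it at the same or a worse grade, nothing in the table changes.

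**4. What cannot be computed**

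The documents give neither the number of subjects who start new therapy within 30 days nor the day on which they start. No expected number of affected events follows from them.

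**The case against.** Five points can fairly be made for the plan.

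*Collection does not stop.* A reader might infer from 6.2.1 that AE collection ends at new therapy. The documents do not support that. The next sentence keeps SAEs and other AEs of concern believed related to study drug, and the Appendix 1 footnote keeps related SAEs. What may be lost is mainly events judged unrelated, and related events that are neither serious nor of concern.

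*The protocol names a governing section.* Section 4.1.3 and the Appendix 1 footnote both point to 6.2.1, and 4.3 can be read as visit scheduling. This makes 6.2.1 the likelier reading at sites. A reader might go further and infer that TEAE rates do mix two windows across sites. That is possible but not shown. Naming 6.2.1 as governing also leaves the mismatch with the SAP in place, and 4.3 still tells sites in plain terms to document new events after new therapy.

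*A share of time at risk would be guesswork.* A reader might try to state the problem as a percentage of the post-dose window or of all time at risk. Every input would have to be assumed. The SAP also tabulates incidences by preferred term and grade, not exposure-adjusted rates.

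*Consequences are limited.* SAP section 5 tests no hypothesis, Phase 2 was not opened, and drug-related TEAEs are tabulated separately. That bears on weight. It does not correct the overall TEAE tables, and the drug-related tables are where the causality filter shows.

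*Versions differ.* The SAP was written to Amendment 2.0. The protocol supplied is later and lists 6.2.1 among its updated sections, so the SAP cannot be checked against the exact text it used. The conflict between 4.3 and 6.2.1 lies within the current protocol and does not depend on this.

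Taken alone, a TEAE window of last dose + 30 days is a legitimate definition. The fault is that the collection rule does not support it.

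**Conclusion.** The concern holds as a mismatch between collection and analysis windows, confined to subjects who start new anticancer therapy within 30 days of last dose. For them, late TEAEs are either filtered by causality or include events arising on the next regimen, depending on which protocol section a site follows. The documents do not reconcile this.

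The number affected is unknown and could be zero. The only size the documents support is per subject: 6.7 points in the 200 mg BID cohort and 11.1 points in the 400 mg QD cohort. This assumes that the subject had no earlier occurrence of the same preferred term on treatment. With safety a primary objective and cohorts this small, the mismatch should be corrected, but it does not invalidate the safety analysis.

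**What to change.** Reconcile protocol 4.3 and 6.2.1 to one AE reporting window, bring the Appendix 1 footnote into line on what is reported afterwards, and make SAP 10.6.1 and 12.2 match.

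The simplest change keeps 6.2.1 as the rule:

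- In SAP 10.6.1, end the TEAE window at the earlier of last dose + 30 days and the start of new anticancer therapy.
- In SAP 12.2, apply the same end point to the cap on imputed AE start dates.
- In protocol 4.3, keep the SFU visit but refer to 6.2.1 for which events are recorded.
- Flag any event recorded after new therapy starts, and list those events separately.

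The alternative is to remove the new-therapy limit from 6.2.1, keep the full 30 days, and tabulate events after new therapy separately. Either is defensible if used throughout.

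The cost is about one sentence per section plus a data flag. No new visit is needed, and SAP 12.2 and 12.3 already use the start of subsequent anticancer therapy. If the data are already collected, the SAP change and the flag can still be made. The downside is slightly fewer late events in the main TEAE tables, and the separate listing keeps those that were recorded visible.
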